6.5.3. Medications/Therapies Allowed During the Study

Classes of medications/therapies that are allowed during the study are recorded as concomitant medications/therapies on eCRF. Participants on certain stable regimens should minimize alteration of the stable regimen during the study. Any changes in stable dosages

and/or regimens should be recorded on eCRF. The permitted medications/therapies are summarized below:

- Stable regimen of non-medicated emollient(s) is permitted during the study to manage dry skin outside of the SD-treated areas. Stable regimen of intranasal/inhaled/ophthalmic corticosteroids;
- Stable regimen of oral (sedating or non-sedating) antihistamine;
- Short courses (≤ 14 days) of oral or parenteral antibiotics if clinically indicated in the judgment of the investigator for the treatment of new onset infections (dermal or non-dermal) not involving SD treatment sites.
- Nonsteroidal anti-inflammatory drugs (NSAIDs), eg, Ibuprofen;
- Concomitant medications for other chronic medical conditions are permitted during the study unless specifically prohibited by the protocol.
- For management of peripheral edema and antecedent co-morbidities, permitted concomitant medications and treatments include the following if regimen has been stable for at least 2 weeks prior to screening:
 - Use of compression therapies;
 - Oral diuretic(s) for management of peripheral edema and/or ascites;
 - Inotropic or chronotropic medications for congestive heart failure;
 - Oral or subcutaneous anticoagulants (eg warfarin, rivaroxaban, dabigatran, apixaban, enoxaparin) for prior DVT,
 - Use of a continuous positive airway pressure (CPAP) device;
 - Use of appetite suppressants;
 - Dietary regimen for weight loss;
 - Oral corticosteroids (no more than prednisone (or equivalent) 15 mg daily) for treatment of chronic non-dermatologic medical condition (eg, COPD, rheumatoid arthritis, nephrotic syndrome, vasculitides, cardiomyopathy).

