5. Has a history of angioedema or anaphylaxis to topical products or known sensitivity to any of the components of the study interventions.
6. History of or active suicidal ideation or behavior, or chronic psychiatric abnormality that may increase the risk associated with study participation or study intervention administration or may interfere with the interpretation of study results and, in the judgment of the investigator, would make the participant inappropriate for entry into this study.
7. Has a history of cancer or has undergone treatment for any type of cancer within 5 years (except squamous cell carcinoma, basal cell carcinoma, or carcinoma in situ of the skin, curatively treated with cryosurgery or surgical excision only).
8. Has received a solid organ (eg kidney, liver, heart, or lung) transplant.

Prior/Concomitant Therapy

9. Has received any of the prohibited medications/therapies that may alter the course of SD without the required minimum washout period or anticipated concomitant use of any of the prohibited medications/therapy (See [Section 6.5.1](#)).
10. Had previous treatment or is currently being treated with crisaborole, or other topical or systemic PDE-4 inhibitor.
11. Participants on biological drugs (eg dupilumab, etanercept, ustekinumab, secukinumab, adalimumab, infliximab) (See [Section 6.5.1](#)).
12. Has a concurrent medical condition which requires use of systemic immunosuppressive agent(s) (See [Section 6.5.1](#) for prohibited medications).

Other Exclusions

13. Has any planned surgical or medical procedure that would interfere with study participation or influence study results.
14. Women of child-bearing potential (WOCBP) are not eligible for this study (See [Appendix 4](#)).
15. Mini-Mental State Examination-2 (MMSE-2, Brief Version) score of <13 (range 0 to 16).
16. Has any of the following laboratory abnormalities confirmed at screening:
Hemoglobin value <9.0 g/dL; Platelet count <100,000/mm³; INR > 3.5; Hemoglobin A1C ≥10.0%.

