6.5.1. Medications Prohibited Prior to Randomization

Classes of medications and non-medication therapies that may alter the course of SD and for which washout is required prior to randomization are listed below. If a participant requires a

washout, the investigator/designee will provide instructions on discontinuing the prohibited medication(s) or non-medication therapy at the screening visit.

Medications Prohibited 12 weeks or 5 half-lives (whichever is longer) Prior to Randomization

- Biological drugs (e.g., dupilumab, etanercept, ustekinumab, secukinumab, adalimumab, infliximab) used primarily for immunosuppressant or immunomodulation to treat a pre-existing chronic inflammatory disease.

Medications/Therapies Prohibited 28 Days Prior to Randomization

- Use of systemic (oral, parenteral) corticosteroids.

Note: Participants on stable use (regular regimen) of intranasal/inhaled/ophthalmic corticosteroids for at least 14 days of intranasal/inhaled/ophthalmic corticosteroids with ≥ 14 days of consistent use prior to randomization are permitted to continue use of intranasal/inhaled/ophthalmic corticosteroids but must not alter or stop their regimen during the study.

- Use of systemic immunosuppressive agents, including but not limited to methotrexate, cyclosporine, tacrolimus, Janus kinase (JAK) inhibitors (eg tofacitinib), azathioprine, 6 mercaptopurine, cyclophosphamide, chlorambucil, rituximab, antilymphocyte globulin, hydroxychloroquine, or mycophenolate mofetil (MMF).

Medications Prohibited 14 Days Prior to Randomization

- Use of oral or parenteral antibiotics for SD.
- Use of topical corticosteroids (TCS) or topical calcineurin inhibitor (TCI) anywhere on the body.
- Use of topical antihistamines anywhere on the body.

Medications Prohibited 7 Days Prior to Randomization

- Use of topical antibacterial medications or products, including soaps, bleach baths, or topical sodium hypochlorite-based products anywhere on the body
- Escalating, decreasing, or as-needed (PRN) use of topical or systemic antihistamines.

Note: Participants on stable dose of oral antihistamines (sedating or non-sedating) for at least 7 days of consistent use prior to randomization are permitted to continue use of oral antihistamines with minimum alteration of dose/regimen during the study.

Medications Prohibited 1 Day Prior to Randomization

- Use of non-medicated emollients (NOTE: can be used on other regions of body, except on lower extremities).

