6.5.2. Medications/Therapies Prohibited During the Study

Classes of medications and non-medication therapies that may alter the SD disease course are prohibited during the study from Day 1 through to the end-of-treatment.

- Biological drugs (eg, dupilumab, etanercept, ustekinumab, secukinumab, adalimumab, infliximab) used primarily for immunosuppressant or immunomodulation to treat a pre-existing chronic inflammatory disease.
- Use of systemic (oral, parenteral) corticosteroids, unless on stable intranasal/inhaled/ophthalmic regimen (see note in [Section 6.5.1](#)).
- Use of TCS or TCI anywhere on the body.
- Use of systemic immunosuppressive agents, including but not limited to methotrexate, cyclosporine, tacrolimus, JAK inhibitors (eg tofacitinib), azathioprine, 6-mercaptopurine, cyclophosphamide, chlorambucil, rituximab, antilymphocyte globulin hydroxychloroquine, or MMF.
- Use of systemic (sedating or non-sedating) antihistamines, unless on stable regimen (see note in [Section 6.5.1](#)).
- Use of any other PDE-4 inhibitor (topical, oral, or parenteral).
- Use of oral or parenteral antibiotics for treatment of infection of SD lesion(s).

Note: Short courses (≤ 14 days) of systemic antibiotics may be given during the study if clinically necessary for the treatment of new onset infections.

- Use of topical antibacterial medications or products, including soaps, bleach baths, or topical sodium hypochlorite-based products on the lower extremities.
- Use of bland (non-medicated) emollients, moisturizers or sunscreen on SD lesions.
- Participation in another drug or device research study.

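### Oral corticosteroids are both allowed and prohibited during treatment, and no passage says which rule governs

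*Protocol*

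**What the plan says.** Four places in the protocol bear on oral corticosteroids.

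- **Section 6.5.3 (allowed during the study)** lists "Oral corticosteroids (no more than prednisone (or equivalent) 15 mg daily) for treatment of chronic non-dermatologic medical condition". The item sits under a lead-in stating that "permitted concomitant medications and treatments include the following if regimen has been stable for at least 2 weeks prior to screening".
- **Section 6.5.1 (28 days before randomization)** prohibits "Use of systemic (oral, parenteral) corticosteroids". Its note makes one exception: participants on stable regimens by the named non-systemic routes "are permitted to continue use of intranasal/inhaled/ophthalmic corticosteroids but must not alter or stop their regimen during the study".
- **Section 6.5.2 (Day 1 to end of treatment)** prohibits "Use of systemic (oral, parenteral) corticosteroids, unless on stable intranasal/inhaled/ophthalmic regimen" and refers back to that same note.
- **Section 5.2, Exclusion 9** excludes a participant who "Has received any of the prohibited medications/therapies that may alter the course of SD without the required minimum washout period or anticipated concomitant use" of such a product. It points to 6.5.1 only.

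For the oral item, 6.5.3 does not refer to the two prohibition lists, and neither list nor Exclusion 9 refers to 6.5.3.

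**The concern.** The permission and the prohibition cover the same drug by the same route over the same treatment days. An investigator who starts from 6.5.3 would enrol a participant on a qualifying regimen and leave it unchanged. One who starts from 6.5.1 and Exclusion 9 would exclude that participant, or give instructions at screening to stop the drug. Section 6.5.1 calls for such stop instructions, whereas the opening of 6.5.3 asks that stable regimens be altered as little as possible.

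Three things are at stake: consistent eligibility decisions, consistent deviation coding, and what a participant is told about a systemic medicine taken for another disease. The situation is foreseeable. Section 2.2 names COPD and chronic kidney disease, with or without nephrotic syndrome, among the conditions predisposing to stasis dermatitis (SD), and 6.5.3 gives COPD and nephrotic syndrome as example indications for the oral corticosteroid.

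**Working it through.** No figure in the plan depends on this point, so there is nothing to reproduce. The check is a comparison of texts plus a day count.

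**Step 1. The rules side by side.**

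| Passage | Period | Oral corticosteroid | Exception stated there |
|---|---|---|---|
| 6.5.1 | 28 days before randomization | Prohibited | Stable intranasal/inhaled/ophthalmic only |
| 6.5.2 | Day 1 to end of treatment | Prohibited | Same, by reference to 6.5.1 |
| Exclusion 9 | At eligibility | Excluded if washout not met or use anticipated | None of its own; refers to 6.5.1 |
| 6.5.3 | During the study | Allowed up to a daily limit, non-dermatologic indication, stable before screening | Not applicable |

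Over the treatment period the overlap of 6.5.2 and 6.5.3 is complete. Neither prohibition expressly covers the days from randomization to Day 1, or follow-up.

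**Step 2. Can a 6.5.3 regimen also satisfy 6.5.1?** If the regimen continues to randomization, it cannot: it is in use within the 28 days. If it is instead stopped at the screening visit, the answer depends on the interval to randomization in the Schedule of Activities (screening Day -28 to -15, randomization Day -7 to -2, each with a ±2-day window).

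- Nominal days: shortest interval = -7 - (-15) = 8 days; longest = -2 - (-28) = 26 days. With 14 screening days and 6 randomization days there are 84 combinations, and none reaches 28. The shortfall is 28 - 26 = 2 to 28 - 8 = 20 days.
- With both windows (Day -30 to -13 and Day -9 to 0): shortest = -9 - (-13) = 4 days; longest = 0 - (-30) = 30 days. Of 18 × 10 = 180 combinations, 6 reach 28 days.

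Those 6 require stopping at screening, which is not a continued stable regimen. A participant who stopped earlier, or who is rescreened under Section 5.4, could meet 28 days, but again not while continuing the regimen.

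**Step 3. Does any text settle precedence?**

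- Another 6.5.3 bullet says: "Concomitant medications for other chronic medical conditions are permitted during the study unless specifically prohibited by the protocol". It is a separate, general item. If it governed the oral corticosteroid item, 6.5.2 would cancel that item for the treatment period.
- Section 6.5 refers questions to the Medical Monitor, but is worded for SD therapy. The 6.5.3 allowance concerns non-dermatologic disease, so this helps only in part.
- Section 5 rules out waivers of enrolment criteria, and Section 4.1 says that meeting any exclusion criterion excludes.

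**Step 4. How does 6.5.2 treat other classes that also appear in 6.5.3?** Five can be counted: emollients, intranasal/inhaled/ophthalmic corticosteroids, antihistamines, systemic antibiotics and oral corticosteroids. For the first four, 6.5.2 itself states a limit or exception, for example "Use of systemic (sedating or non-sedating) antihistamines, unless on stable regimen". For oral corticosteroids it states none.

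**The case against.** The strongest reply is that 6.5.3 is a specific exception to a general ban. It names the drug, a dose ceiling, an indication class and a stability condition, and reading it this way gives effect to both texts. If the ban prevailed, the item would allow nothing during treatment. This reading is possible, but the protocol does not state it. Section 6.5.2 has its own corticosteroid clause that leaves oral use out, and Exclusion 9 sends the reader only to 6.5.1.

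Parts of the reply stand:

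- The count of four in five is soft. By bullet, 6.5.2 has four overlapping entries, since both corticosteroid classes share one. The antibiotic limits differ between the sections (6.5.3 adds a restriction on infection site), as do the emollient limits (lesions against treated areas). The intranasal/inhaled/ophthalmic clause may only clarify scope, since those routes lie outside oral and parenteral use. The count is supporting evidence; the contradiction does not depend on it.
- Exclusion 9 derives from 6.5.1 and is not an independent ban.
- Clarifying which text applies would not be a waiver, and this trial has already issued administrative change letters for clarifications.
- The analysis consequence is limited. Neither document defines a per-protocol set, the full analysis set includes everyone randomized who applied a dose, and concomitant medication is recorded and summarised by treatment group.

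**Conclusion.** The concern holds, and the protocol is wrong as written on this point. Two stated rules give opposite eligibility decisions and opposite continue-or-stop instructions for the same participant, so sites cannot follow both. It should be fixed.

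Its size is operational. The documents give no frequency of oral corticosteroid use, so the number affected is unknown and may be zero. Eligibility is settled before assignment and the study is blinded, so the validity of the randomized primary comparison is not in question, and no effect on the treatment difference or power is claimed.

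The conclusion rests on the current wording of the four passages and on the absence of any cross-reference or precedence statement. The day count in Step 2 is secondary: the conflict over the treatment period exists whatever the screening interval.

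**What to change.** Reconcile Sections 6.5.1, 6.5.2, 6.5.3 and Exclusion 9 so that they state one rule on oral corticosteroids, with each passage referring to the others. Which rule that should be is a clinical decision for the sponsor, and none is proposed here.

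If the reconciled text keeps a washout, check it against the scheduled screening-to-randomization interval, allowing for the visit windows, for participants who stopped before screening and for rescreening.

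The cost is one wording clarification across four passages, with the usual IRB/IEC review. No new data are needed, and the primary analysis and sample size do not change. A sensitivity analysis excluding participants with oral corticosteroid use ongoing at randomization is optional and not part of the required change.

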6.5.4. Rescue Medicine

No rescue medications (eg, corticosteroids, calcineurin inhibitors, or other PDE4 inhibitors) are permitted for SD during treatment with study intervention.

In the event of worsening SD, the Investigator may determine that an unplanned safety visit (telemedicine assessment or face-to-face assessment (by HVP or a local HCP) is indicated.

6.6. Dose Modification

Dose Modification is not permitted in this study. Study intervention must be applied BID at the targeted application rate (approximately 3 mg/cm²).

6.7. Intervention after the End of the Study

There is no intervention required by the protocol following the end of study. Participants should resume their usual medical care.

7. DISCONTINUATION OF STUDY INTERVENTION AND PARTICIPANT DISCONTINUATION/WITHDRAWAL

At the discretion of the Investigator, study intervention may be temporarily or permanently discontinued. In the event of a participant being hospitalized for management of a chronic medical condition, study intervention must be permanently withdrawn.

If an IA (described in [Section 9.4](#)) is performed and the IRC recommends ending the study because of futility, participants in the screening phase may be discontinued from the study based on sponsor decision. If a futility threshold is crossed based on the IA results, participants may be withdrawn from study treatment, complete an early termination visit, and complete the study follow-up phase.

Participants may be discontinued due to study termination (as described in [Section 10.1.9](#)).

7.1. Discontinuation of Study Intervention

In rare instances, it may be necessary for a patient to permanently discontinue study intervention. If study intervention is permanently discontinued, the participant should continue to complete all scheduled assessments at the EOT visit and complete the follow-up phase of the study.

Note that discontinuation of study intervention does not represent withdrawal from the study.

If a clinically significant finding is identified (including, but not limited to, changes from baseline in QT interval corrected using [Fridericia's formula \[QTcF\]](#)) after enrollment, the investigator or qualified designee will determine if the participant can continue in the study and if any change in participant management is needed. This review of the ECG printed at the time of collection must be documented. Any new clinically relevant finding should be reported as an AE. Discontinuation of study intervention for abnormal liver function should be considered by the investigator when a participant meets one of the conditions outlined in [Appendix 5](#) or if the investigator believes that it is in best interest of the participant.

If signs and symptoms of hypersensitivity are attributable to the study intervention, including contact urticaria, it must be discontinued immediately, and appropriate therapy initiated.

If skin ulcer(s) develop in any of the SD treatment areas, then study intervention must be permanently discontinued. If skin ulcer (s) develop in any of the untreated areas (including an untreated leg in the case of unilateral disease), study medication may continue at the discretion of the investigator.

If an unscheduled ECG is necessary after randomization to evaluate an AE, discontinuation of study ointment should be considered if the QTcF interval on the unscheduled ECG is \geq 481 msec or if there is an increase in the QTcF interval of \geq 60 msec in comparison to the QTcF interval on the ECG completed during screening. This review of the electrocardiogram (ECG) at the time of collection must be documented. Any new clinically relevant finding should be reported as an AE.

See the [Schedule of Activities](#) (SoA) for data to be collected at the time of intervention discontinuation and follow-up and for any further evaluations that need to be completed.

7.1.1. Temporary Discontinuation

Participants who experience medical conditions that require treatment (not prohibited concomitant medications) may have their study intervention temporarily discontinued for <6 days after consultation with the Pfizer medical monitor. Temporary discontinuation of study intervention should be recorded in the eCRF.

7.2. Participant Discontinuation/Withdrawal from the Study

- A participant may withdraw from the study at any time at his/her own request, or may be withdrawn at any time at the discretion of the investigator for safety, behavioral, compliance, or administrative reasons. This is expected to be uncommon.
- At the time of discontinuing from the study, if possible, an early discontinuation visit should be conducted, as shown in the [Schedule of Activities](#). See [Schedule of Activities](#) for data to be collected at the time of study discontinuation and follow-up and for any further evaluations that need to be completed.
- If the participant withdraws consent for disclosure of future information, the sponsor may retain and continue to use any data collected before such a withdrawal of consent.
- If a participant withdraws from the study, he/she may request destruction of any samples taken and not tested, and the investigator must document this in the study records and notify the sponsor accordingly.
- When a participant withdraws from the study because of an SAE, the SAE must be recorded on the CRF and reported on the CT SAE Report.

7.3. Lost to Follow up

A participant will be considered lost to follow-up if he or she repeatedly fails to complete a scheduled telemedicine visits and is unable to be contacted by the study site.

The following actions must be taken if a participant fails to complete a required telemedicine visit:

- The site must attempt to contact the participant and reschedule the missed visit as soon as possible and counsel the participant on the importance of maintaining the assigned visit schedule and ascertain whether the participant wishes to and/or should continue in the study.
- Before a participant is deemed lost to follow up, the investigator or designee must make every effort to regain contact with the participant (where possible, 3 telephone calls and, if necessary, a certified letter to the participant's last known mailing address or local equivalent methods). These contact attempts should be documented in the participant's medical record.
- Should the participant continue to be unreachable, he/she will be considered to have withdrawn from the study.

Discontinuation of specific sites or of the study as a whole are handled as part of [Appendix 1](#).

8. STUDY ASSESSMENTS AND PROCEDURES

In addition to the 3 scheduled HVP home visits, assessments will be conducted by the Central Investigator Group (CIG) and Remote Trial Coordinator (RTC) through telemedicine (videoconferencing for the purposes of this study) interviews with the participant. The first telemedicine interview will occur at randomization ([Section 1.3.1](#)). A telephone only interview is permitted in the event of technical difficulties which preclude video component.

During the intervention period, telemedicine interviews with the participant will be conducted by the RTC; the CIG may attend if requested by the RTC or if the Investigator chooses to attend.

End of treatment (EOT) home visit (Week 6 or Early Termination) will be conducted by the HVP. In addition, telemedicine interviews may be conducted by the CIG with the participant (see [Schedule of Activities](#)) if adverse event(s) assessment is indicated in the judgment of the investigator.

Further specifications for study assessments and procedures include:

- The CIG and RTCs will perform all the rater assessments except for the scoring of TSS, ISGA, and lesional %BSA which will be performed by the HVP (in-person assessment at screening visit, training visit, Week 6 or early termination visit, and unplanned safety assessment) and by a Central Reader (at scheduled weekly digital image acquisition timepoints and at unplanned telemedicine visits [if any]). See [Appendix 6](#) for information on VRCT.
- Study procedures and their timing are summarized in the [Schedule of Activities](#). Protocol waivers or exemptions are not allowed.

- Immediate safety concerns should be discussed with the sponsor immediately upon occurrence or awareness to determine if the participant should continue or discontinue study intervention.
- Unplanned safety assessments may be conducted during the study using telemedicine interviewing to assess any ongoing or new onset safety events. The CIG will be present for any unplanned safety telemedicine interview. If an AE is suspected or determined to have occurred, then the CIG can recommend in person clinical evaluation by an HVP or referral to the participant's local HCP or subspecialist if warranted in the clinical judgement of the CIG. If a determination is made that the participant's medical condition warrants urgent evaluation, then the/ participant may be directed to urgent care or emergency department evaluation.
- Adherence to the study design requirements, including those specified in the [Schedule of Activities](#), is essential and required for study conduct.
- All screening evaluations must be completed and reviewed to confirm that potential participants meet all eligibility criteria. The investigator will maintain a screening log to record details of all participants screened and to confirm eligibility or record reasons for screening failure, as applicable.
- Procedures conducted as part of the participant's routine clinical management (eg, blood count) and obtained before signing of the ICF may be utilized for screening or baseline purposes provided the procedures met the protocol-specified criteria and were performed within the time frame defined in the [Schedule of Activities](#).
- The maximum amount of blood collected from each participant over the duration of the study, including any extra assessments that may be required, will not exceed 25 mL. Repeat or unscheduled samples may be taken for safety reasons or for technical issues with the samples.

